Recording and reporting of adverse events that occur during the course of the study will help to ensure the continuing safety of participants. Local and systemic adverse events will be monitored during the study.

In case an adverse event does take place, a documentation system will be used to record the following information: description of event, time/date of onset, duration of reaction, relationship to study proceedures/drug, and seriousness/severity (based on Common Terminology Criteria for Adverse Events v4).

Study stoppage will occur if 40 subjects complete the study or if a severe adverse event related to the study occurs.

The PI will be responsible for monitoring ongoing activates to ensure compliance with regulator ad protocol requirements, data quality, and participant safety.

For MRI measurement

Privacy: Subjects to be scanned in the Imaging Facility are given a unique identifier, consisting of the first four letters of the investigator's PSY login name, a five-character study code, and the subject's participant number (up to 8 digits) as assigned by each research team. For example, AJHA

PI: [name]

IRB Study Number: 20200857

NCT04717466

Version 9, Date: 21Mar2024

_MIND_03, JBRI__ABMT_40001 codes may be used. This Facility code is the "name" to be entered in the MR computer file. No actual name nor any other identifying information is to be entered in the MR computer file, to make certain that subject privacy can be fully observed. Individual investigators are responsible for keeping records in order to identify the raw data collected in the Facility.

Safety screening: In Zone II (bathroom and waiting area of the MRI environment), research participants will complete a metal screen and remove all metal objects. Women must remove their underwire bras. Gowns are provided, if desired. After reviewing these forms, the MRI technologist will determine if the research participant is eligible to scan. The original forms will be kept in a locked file cabinet and filed according to date in the MRI facility and a copy will be given to the investigator.

Incidental findings: [name] [name] (Associate Professor of Radiology, Neuroradiology section and Medical Director of the Applebaum Diagnostic Imaging Center) will review a baseline structural scan from each subject that undergoes an MRI for any incidental findings. She will generate a summary report and the PI will communicate any results of clinical significane to the subject. Also a copy of this MRI summary report will be provided to the subject to all them in order to communicate the findings with their medical doctor. The subject may also request a DVD of their brain images.

13) Withdrawal of Subjects*

All subjects are free to withdraw from participation in this study at any time, for any reason, and without prejudice.

Subjects must be withdrawn from the study if:

- 1) A subject withdraws consent.
- 2) The Investigator believes it is in the best interest of the subject to be removed from the study.
- 3) If the subject experiences greater than a mild adverse event. (Subjects that experience a mild adverse event will be asked if they would like to continue the study. The occurrence of a severe adverse event will trigger the study to stop for safety purposes.)
- 4) Failed COVID-19 checks, including COVID-19 screening questionnaire and temperature check, required by the MRI facility.

The data collected before the withdrawal will still be used in data analysis.

PI: [name]

IRB Study Number: 20200857

NCT04717466

Version 9, Date: 21Mar2024

14) Risks to Subjects*

1. MRI.

There are no foreseeable risks to a participant as all measures have been taken to ensure their safety. The participant may only run the risk of feeling claustrophobic when they are within the MRI scanner. All participants will be given the opportunity to experience the scanner in a mock environment.

Magnetic fields do not cause harmful effects at the levels used in the MRI

Magnetic fields do not cause harmful effects at the levels used in the MRI machine. However, the MR scanner uses a very strong magnet that will attract some metals and affect some electronic devices. If the participant has a cardiac pacemaker or any other biomedical device in or on your body, it is very important they you tell the operator/investigator immediately. As metallic objects may experience a strong attraction to the magnet, it is also very important that they notify the operator of any metal objects (especially surgical clips), devices, or implants that are in or on their body before entering the magnet room. All such objects must be removed (if possible) before entering the magnet room. In some cases, having those devices means you should not have an MRI scan performed. In addition, watches and credit cards should also be removed as these could be damaged. The participant will be provided a way to secure these items. If the participant has any history of head or eye injury involving metal fragments, if they have ever worked in a metal shop, or if they could be pregnant, they should notify the operator/investigator.

There is a possibility the participant will experience a localized twitching sensation due to the magnetic field changes during the scan. This is expected and should not be painful. Dizziness or nausea may occur if you move your head rapidly within the magnet.

IF THE PARTICPANT FEELS DISCOMFORT AT ANY TIME, THEY CAN NOTIFY THE OPERATOR AND CAN DISCONTINUE THE EXAM AT ANY TIME.

The scans performed in this study are for specific research purposes and are not optimized to find medical abnormalities. The investigators for this project may not be trained to perform medical diagnosis. The investigators are not responsible for failure to find existing abnormalities with these MRI scans. However, on occasion the investigator may notice a finding on an MRI scan that seems abnormal. When this occurs, a physician will be consulted as to whether the findings merit further investigation, in which case the investigator will contact you and your primary care physician and inform you of the finding

PI: [name]

IRB Study Number: 20200857

NCT04717466

Version 9, Date: 21Mar2024

(NeuroscienceMRI_Notification form). The decision as to whether to proceed with further examination or treatment lies solely with you and your physician. The investigators, the consulting physician, and the University of Miami are not responsible for any examination or treatment that you undertake based on these findings. Because the images collected in this study may not comprise a proper clinical MRI scan, these images will not be made available for diagnostic purposes.

Women of Childbearing Potential: If any participant is pregnant or currently breast-feeding, they may not participate in any of our studies involving MRIs. The participant must understand that if they are pregnant or become pregnant, or if they are breast-feeding during this study, themselves or their child may be exposed to an unknown risk.

- 2. Injection of Secukinumab: The injection of Secukinumab may increase the risk of infection. Patients may experience nasopharyngitis, diarrhea, and upper respiratory tract infection.
- 3. Protected Health Information (PHI). Protected Health Information (PHI) will be collected during the study. Every attempt will be made to ensure that this PHI is kept secure. All study data will be kept in a locked office and kept under password protection on a computer that is only accessible by study personnel.

15) Potential Benefits to Subjects*

Psoriasis patients will receive a potent anti-psoriatic biologic.

16) Vulnerable Populations*

No vulnerable populations will be enrolled in this study.

17) Setting

The pre-study visit will be conducted at the Dermatology Clinical Trial Unit at the University of Miami Medical campus.

Research will be conducted in the neuroscience annex at the University of Miami, Florida. Data acquisition will be conducted using 3T MRI located within the neuroscience annex.

PI: [name]

IRB Study Number: 20200857

NCT04717466

Version 9, Date: 21Mar2024

Potential subjects will be identified and recruited through IRB approved flyers.

18) Resources Available

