- 18) Diagnosis of a major psychiatric disorder such as schizophrenia, major depression or bipolar disorder that is active currently.
- 19) Morbid obesity
- 20) Weight: 250 lb or more
- 21) Any known diseases or disorders that may affect conducting the experiments (e.g., intracranial pathology, claustrophobia, severe respiratory or cardiovascular problems, active fibromyalgia) or diseases that have potential risks of infections (e.g., HIV, Hepatitis C, etc).
- 22) Inability to speak and read English.
- 23) Pregnant.
- 24) Incarcerated.

6) Number of Subjects*

This is an exploratory study to elucidate brain mechanisms associated with perceptions of well-being and improvements in itch and/or pain after use of a potent effective treatment for psoriasis using IL-17 neutralization. We will enroll 15 psoriasis patients and 15 healthy subjects with an approximately equal gender distribution, in order for 10 psoriasis patients and 10 healthy subjects to complete the study.

Psoriasis patients will be recruited from the Department of Dermatology Clinics. An approximately equal number of men and women between 18 and 65 years of age will be recruited using IRB-approved advertising. All participants will be required to consent and to fulfill the inclusion and exclusion criteria. Healthy subjects (similar age and gender ratio to the patient group) will be recruited through IRB-approved advertisement. UM students or employees may be enrolled in this study as long as they fulfill the inclusion and exclusion criteria.

7) Recruitment Methods*

Patients seen for their routine care at the Dermatology Outpatient Clinics at the University of Miami Hospital, South Miami satellite site, and Lennar Medical Foundation satellite site will be identified for possible study eligibility by any of the dermatologists in our practice. If the treating dermatologist is a study team member, they will ask the potential subject if they would be interested in being contacted by the study team to learn

PI: [name]

IRB Study Number: 20200857

NCT04717466

Version 9, Date: 21Mar2024

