Assessment of how an effective biologic treatment of psoriasis (Secukinumab) improves the patient's quality of sleep by using the Numerical Rating Scaling (NRS) rainging from 0 to 10, with a higher score indicating lower sleep quality between baseline, 1 week (visit 2), and 4 weeks (visit 3) as well as by comaparing between the patient and healthy control group.

Assessment of how an effective biologic treatment of psoriasis (Secukinumab) improves the patient's physical activity by using the 7-days physical activity recall (7D-PAR) ranging from 0 to 27, with a higher score indicating more physical activity between baseline, 1 week (visit 2), and 4 weeks (visit 3) as well as by comaparing between the patient and healthy control group.

Assessment of how an effective biologic treatment of psoriasis (Secukinumab) improves stress in daily life in psoriasis patients by using the Perceived Stress Questionnaire (PSQ) ranging from 0 to 1, with a higher score indicating more stress between baseline, 1 week (visit 2), and 4 weeks (visit 3) as well as by comaparing between the patient and healthy control group.

10) Schedule of Assessments

10 patients with psoriasis and 10 healthy controls will participate in this study. The patient group will have 3-4 study visits and 1 follow up visit, while the healthy control group will have 3 study visits (Fig. 1). Patients can be rescreened in a washout period is needed.

Pre-Study visit (Patients only)

- *Patients that have not had a TB preformed in the past 8 months will have to attend this pre-study visit to undergo a TB test
 - Patients will fill out an informed consent
 - Assessment of Body Surface Area (BSA) to show percent of psosiais involvement from 0 to 100%.
 - Blood (~4ml) will be drawn for the Quantiferon TB Gold test
 - Subjects can not proceed to the 1st study baseline visit until results are received

PI: [name]

IRB Study Number: 20200857

NCT04717466

Version 9, Date: 21Mar2024

- If an indeterminate result is received, the subject will be offered to repeat the test once
- If a positive result is received, the subject will be excluded from the study and refered to their primary care physician for further assessment and/or treatment
- If a negative result is received, the subject may continue with the study

1st study visit (Baseline measurements)

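### Section 13, criterion 4 makes a failed MRI-facility COVID-19 check a mandatory study withdrawal, so a failure at visit 2 or 3 also forfeits later visits; it also conflicts with criterion 3

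*Combined protocol and SAP*

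**What the plan says.** Section 13 (Withdrawal of Subjects) opens its list with "Subjects must be withdrawn from the study if", and item 4 of that list is "Failed COVID-19 checks, including COVID-19 screening questionnaire and temperature check, required by the MRI facility". The section gives no number of failures, no confirmatory test and no repeat of the check.

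Item 3 of the same list withdraws anyone whose adverse event is more than mild. It adds that subjects with a mild event are to be asked whether they wish to go on.

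On data, the section states: "The data collected before the withdrawal will still be used in data analysis". Nothing provides for collecting data after withdrawal. The only re-entry route in the protocol is in Section 10 and concerns washout: "Patients can be rescreened in a washout period is needed".

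Section 10 schedules MRI at baseline, week 1, week 4 and the three-month follow-up for patients, and at the first three of these for controls. Visits 2, 3 and the follow-up each have a window of ± 3 days. Patients also complete itch and pain NRS, PASI, WHO-5, sleep NRS, 7D-PAR and PSQ at these visits; controls complete the last four.

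Section 6 plans for losses: "We will enroll 15 psoriasis patients and 15 healthy subjects", "in order for 10 psoriasis patients and 10 healthy subjects to complete the study". Section 14 warns that secukinumab may raise the risk of infection and continues: "Patients may experience nasopharyngitis, diarrhea, and upper respiratory tract infection".

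**The concern.** The check is described as a requirement of the MRI facility. Not scanning the participant that day would meet that requirement. Criterion 4 goes further and removes the participant from the study. A raised temperature at week 1 then costs not only the week-1 scan but also the week-4 scan, which is a primary time point, and for patients the three-month follow-up. It ends the clinical and questionnaire measures too, although none of them depends on the scanner.

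With 10 completers wanted per group, each avoidable loss counts. The rule also sits badly beside criterion 3. A participant with a mild cold and a raised temperature has a mild event, and so may choose to continue under criterion 3, but must leave under criterion 4.

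**Working it through.** **The plan's own figure.** The only attrition figure is 15 enrolled for 10 completers per group, an allowance of 15 − 10 = 5, or 5/15 = 33.3%. No dropout rate is stated. Recovering 15 as 10/(1 − 1/3) is therefore circular and does not test the figure. Criterion 4 disputes no number in the plan; the question is what it adds to the losses.

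**Which failures forfeit later visits.**

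- Baseline: the scan comes before the first injection, so a failure here is a lost or delayed enrolment and not an effect of treatment.
- Patients after baseline: failures at visits 2 and 3 forfeit something later. A failure at the follow-up does not, because nothing follows it.
- Controls after baseline: only a failure at visit 2 does, because visit 3 is their last.

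**Inputs.** Group size 15 (Section 6), taken as all having passed the baseline check. Visit schedule from Section 10. The failure probability *p* per visit is not in the documents; it is assumed to be 1%, 2% or 5%, equal in both groups and independent across visits.

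**Participants who lose later visits.** Patients: 1 − (1 − *p*)². Controls: *p*.

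| *p* | Patients | of 15 | Controls | of 15 |
|---|---|---|---|---|
| 1% | 1 − 0.99² = 2.0% | 0.30 | 1% | 0.15 |
| 2% | 1 − 0.98² = 4.0% | 0.59 | 2% | 0.30 |
| 5% | 1 − 0.95² = 9.8% | 1.46 | 5% | 0.75 |

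**Post-baseline patient scans lost, of 3.** Under withdrawal the expected loss is 3 − [(1 − *p*) + (1 − *p*)² + (1 − *p*)³]. If only the affected scan is missed, it is 3*p*.

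- *p* = 1%: 3 − (0.990 + 0.980 + 0.970) = 0.06, against 0.03.
- *p* = 5%: 3 − (0.950 + 0.903 + 0.857) = 0.29, against 0.15.

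The withdrawal rule therefore loses about twice as many post-baseline patient scans as a missed-scan rule. At 5%, over 15 patients, that is about 4.4 scans against 2.3 (15 × 0.290 and 15 × 0.15). Any successful rebooking would lower the second figure further.

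**What the group comparison shows.** The same *p* is used in both groups, so the gap between 9.8% and 5% comes only from patients having one more visit at which a failure forfeits something. It says nothing about infection. A gap due to the drug would need a higher *p* in patients, and the documents give no figure for that. As an illustration only, doubling the patients' rate from 5% to 10% would give 1 − 0.90² = 19% against 5%.

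**The case against.** **The text does not say that one failure excludes someone for good.** A reader might infer this. Criterion 4 speaks of checks in the plural, gives no count, and is silent on repeating a check within the window; silence is not prohibition. This stands as a limit on the wording. It does not remove the point, because the governing sentence is mandatory, any failure meets it as written, and no route back is given.

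**Selective loss is not shown.** A reader might infer that the rule preferentially drops treated patients with infections. Section 14 makes this plausible, but it says only that risk may rise and gives no rate. Criterion 3 already removes anyone with a more than mild event, so criterion 4 adds mainly mild illness and positive questionnaires. This objection stands in full.

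**Counting all scans overstates the harm.** Over four patient scans, 1 − (1 − *p*)⁴ gives 3.9% to 18.5% at 1% to 5%, or 0.6 to 2.8 of 15. That count includes baseline, before any drug, and the follow-up, after which nothing is lost. Even 2.8 is below the allowance of 5.

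**A milder rule does not restore the missed time point.** With ± 3 days, some scans cannot be rebooked, and PASI at that visit cannot be recovered by a remote questionnaire. Section 11 names a two-way ANOVA for the clinical scales and gives no method for missing data. This is right, and the fix must include the analysis. Later visits are still worth keeping.

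**Injections are given at the end of visits 1 to 3**, so changing the rule touches treatment. This too is right, and the recommendation is confined to data collection.

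**Conclusion.** The point holds as a minor design fault. Criterion 4 requires withdrawal where cancelling a scan would meet the facility's requirement. It thereby forfeits later scans and scanner-free assessments after a failure at visit 2 or 3. Criteria 3 and 4 give different outcomes for the same subject with a mild event and must be reconciled.

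The size rests on an assumed failure rate. At 1% to 5% per visit, about 2% to 10% of patients (0.3 to 1.5 of 15) and 1% to 5% of controls (0.15 to 0.75 of 15) would lose later visits, against an allowance of 5 per group. The documents do not support the conclusion that the completer target is in danger from this rule alone at those rates, or that treatment-related dropout has been demonstrated.

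**What to change.** For data collection only, reword criterion 4 along these lines: a failed facility check cancels that day's scan; the scan is rebooked inside the visit window if possible and otherwise recorded as missing; questionnaires are collected remotely where feasible; and the participant remains scheduled for later visits. Reconcile this with criterion 3, so that a mild event leads to one stated outcome for study participation.

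Add a sentence to Section 11 on how participants with a missing scan are analysed. One example is a mixed model using all available visits, applied to the clinical scales and to values from the brain regions that the baseline comparison identifies. The same sentence would give effect to the commitment in Section 13 to use data collected before withdrawal.

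Whether study drug continues after a failed check is a clinical decision for the investigator, and nothing is proposed on it here.

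The cost is two or three sentences in an amendment, some rebooking effort, and some incomplete scan series in the analysis.

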Research Fellows and Student Researchers from the Department of Dermatology & Cutaneous Surgery at the University of Miami will assist in subject recruitment, and study procedures, and data entry. They will be CITI certified and approved in the IRB system.

All study personnel will complete their CITI training and be adequately informed about the protocol and study procedures. All duties and functions are appointed and overseen by the PI.

19) Confidentiality

Protected Health Information (PHI) will be collected, but will not be disclosed. Therefore, a HIPAA authorization form will be collected. Every attempt will be made to ensure that this PHI is kept secure. All study data will be kept in a locked office and kept under password protection on a computer that is only accessible by study personnel.

All data, documents, reports, and scans (not including consent and demographic documents) will be kept de-identified and coded with a link between the code and subject's identity maintained separately from the data. Only the PI will have access to the code sheet. PHI (name and DOB) will be kept on UM's Velos system in order to track the subject's study status.

Data will be stored on a UM electronic device (encrypted, password-protected computer) and no data, documents, reports, or scans will be sent outside of UM.

EMR or PHI without obtaining a signed HIPAA authorization from the subject will be accessed to identify potential subject for recruitment purposes only. The PI confirms that the information collected for this will be destroyed or de-identified at the earlier opportunity. Information collected for this purpose will not be reused or disclosed to any other person or entity, except as required by law, for authorized oversight of the research study or for other research for which the use of disclosure of PHI is permissible.

- Study #: 20200857 Effective Date: 4/16/2024

PI: [name]
IRB Study Number: 20200857
NCT04717466

Version 9, Date: 21Mar2024

Choose the statements below that are applicable to this research:

26(a). Will the research collect protected health information or personall information from the EMR or from subjects at UHealth and/or IHS?

26(a). Will the research collect protected health information or personally identifiable information from the EMR or from subjects at UHealth and/or JHS? Yes (If checked go to 26(b)) No (If checked, go to Section 27) 26(b). Check the box next to the correct statement below Research Subjects will sign a HIPAA Authorization before the research will collect this data. Research Subjects will not sign a HIPAA Authorization for this data collection and the research is requesting a waiver of HIPAA authorization from the IRB. 26(c). How will the research store the data? On a University of Miami electronic device (e.g. encrypted, password-protected computer) ☑ On a cloud-based storage system that is approved by the University of Miami On the secured JHS SharePoint environment 26(d) Select one of the following: The Principal Investigator (and/or Study Team members) will record (e.g. write down, abstract) data acquired in a manner that does not include any indirect or direct identifiers (listed in the instructions for Section 26 of this protocol), and the recorded data will not be linked to the individual's' identity. The Principal investigator (and/or Study Team members) will record (e.g. write down, abstract) the data collected in a manner that does not include any direct identifiers (see list in the instructions for Section 26 of this protocol) of any subject. Instead, the Principal Investigator and/or Study Team members shall will assign a code (that is not derived in whole or in part from any direct or indirect identifiers of the individual) to each study subject and link the code to the study subject's identity. The link to each subject's identity and/ or other identifiable information will be maintained on a document separate from the research data. 26(e) Additional requirement for Jackson Health System Data: Not-applicable, no data will be acquired from JHS under a waiver of authorization. ☐ JHS data, including Protected Health Information (PHI) and/or Personally Identifiable Information (PII), acquired from JHS for this research under a waiver of authorization shall only be stored on the secured JHS SharePoint environment made available by JHS. I and

the Study Team members shall not copy or store the JHS sourced personally identifiable

PI: [name]

IRB Study Number: 20200857

NCT04717466

Version 9, Date: 21Mar2024

information (PII), including protected health information (PHI) data to any other system, including any systems maintained or provided by the University of Miami. I and the Study Team shall only copy or transfer JHS-sourced data that has been properly de-identified in accordance with all requirements contained in the HIPAA Rules by removing all of the identifiers listed in the instructions for Section 26 of this protocol.

20) Biospecimens

\boxtimes	Not applicable. No biospecimens will be collected
	Bio -Specimens obtained for this research will be stored without any direct or indirect identifiers.
	Bio -Specimens obtained for this research will be stored in a de-identified coded manner.
m	When required to transport data or bio-specimens for this research, the research am will transport the data and bio-specimens in a de-identified (or anonymous) anner with a link to the individual subject's identity maintain separately from the ata and/or bio-specimen.

21) Provisions to Protect the Privacy Interests of Subjects

Study subjects will only be asked to provide personal information to approved study personnel, who will ensure the subject is at ease with the situation. Study personnel will clearly explain that the subject does not have to answer any questions or provide any sample they are uncomfortable about.

22) Compensation for Research-Related Injury

There is no available compensation in the event of research related injury.

23) Economic Burden to Subjects

There will be no charges to the subjects that agree in participating in this study.

24) Consent Process

The research team will follow the "HRP-090 SOP: Informed Consent Process for Research" to obtain informed consent and the "HRP-091 SOP: Written Documentation of Informed Consent" to document informed consent in writing.

PI: [name]

IRB Study Number: 20200857

NCT04717466

Version 9, Date: 21Mar2024

Study personnel will meet with each potential subject to discuss the study in detail, answer questions, and allow the subject to read the entire consent form. The informed consent form explicitly states the rationale for the study and requirements for participation, both before and during the session. The informed consent form states that subjects may discontinue participation or be terminated from the study at any time.

All pertinent aspects of the study will be explained to the subject before he or she signs the informed consent form. A signed informed consent form will be obtained from the subject before any activity or treatment is undertaken as part of the study.

Non-English Speaking Subjects will not be enrolled. Subjects who are not yet adults (infants, children, teenagers), cognitively impaired adults, and adults unable to consent will not be enrolled.

This trial will be registered on ClinicalTrials.gov.

25) Process to Document Consent in Writing

The research team will follow the "HRP--091 SOP: Written Documentation of Informed Consent" to document informed consent in writing.

26) Authorization for Use and Disclosure of Protected Health **Information (HIPAA)**

Type of Request: Waiver of Authorization for access to medical record for subject identification/recruitment. Waiver of Authorization for access to medical record to obtain data for the research.
Confirm that you will destroy the Protected Health Information (PHI) you and/or your Study Team acquire receive from JHS and/or UHealth at the earliest opportunity. I confirm
Confirm that the Protected Health Inform (PHI) you acquire from JHS and/or UHealth will not be re-used or disclosed to any other person or entity, except as required by law or for authorized oversight of the research study or for other research for which the use or disclosure of PHI is permissible. I confirm
 ot applicable. This research will not collect data from JHS record under a waiver of orization

PI: [name]

IRB Study Number: 20200857

NCT04717466

Version 9, Date: 21Mar2024

Notwithstanding the preceding "I confirm" statements above, I agree that neither I nor any member of the study team listed on the IRB submission for this Protocol shall ever re-use or re-disclose any of the information acquired from Jackson Health System in any format, whether **identifiable or de-identified**, to any individual or entity without first obtaining written permission from Jackson Health System, even if such re-use or re-disclosure is permissible by law (e.g., HIPAA).

27) Drugs or Devices

Secukinumab will be given to psoriatic subjects as per the FDA approved label.

28) References

